Postoperative pain that persists beyond the normal time for tissue healing is increasingly recognized as an important complication after various types of surgery. According to the International Association for Study of Pain, CPSP is defined as the persistence of pain at surgical site or referred area, at least 3 months following the surgical procedure.⁹ CPSP is common after cardiac surgery. The reported incidence was 28% to 56% up to 2 years postoperatively.¹⁰⁻¹² Several mechanisms have been involved in the development of chronic pain after sternotomy. These include dissection, nerve entrapment by sternal wires, sternal retraction, ribs fractures, and intercostal neuralgia as a consequence of nerve damage during dissection of the internal mammary artery during coronary artery bypass graft (CABG).²⁻³ In addition, poorly controlled pain has been a general risk factor for the development of CPSP. All can stimulate the release of pro-inflammatory cytokines which sensitize the afferent nociceptive fibres to cause chronic pain. CPSP has the potential to impact daily functioning and quality of life of patients, as well as increasing the healthcare costs. CARDpain study reported that among those with CPSP, over 50% had significant pain-related interferences with activities of daily living (family and home responsibilities, recreation and employment) at 3, 6 and 12 months following cardiac surgery.¹³ Therefore, apart from optimal acute pain control, it is equally

important to prevent and manage CPSP, to ensure better satisfaction and quality of lives for our patients.

CHALLENGES IN PAIN MANAGEMENT

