Intravenous opioids such as fentanyl and morphine have been the mainstay of perioperative analgesia for cardiac surgery, either by intermittent boluses or through a patient-controlled device. The primary problem with this mechanism of delivery is that significant fluctuations in serum opioid concentrations can occur, resulting in effects which range from inadequate analgesia to overdose and respiratory depression. These peaks and troughs of analgesia that occur with intermittent opioids administration may explain the suboptimal pain control during the initial postoperative period. In contrast to intermittent administration of short-acting opioids such as morphine and fentanyl, a single dose administration of methadone can be considered. Methadone was conventionally used in cancer and chronic pain management. It can be administered via oral, intravenous, and other parenteral routes. Despite being an often-used alternative to morphine, it remains relatively invisible in perioperative settings. Methadone is a unique opioid that may provide several important potential benefits for surgical patients in the perioperative period. It is a potent mu receptor agonist with a rapid onset and longest half-life (24-36 hours) of the clinically used opioids. According to a pharmacokinetic study,¹⁴ central nervous system effect site methadone concentration rapidly equilibrates with plasma concentrations, evidenced by a short lag time between plasma concentrations and effects ($t_{1/2}k_{e0}$ 4min). This is comparable to the rapid onset and effect compartment equilibration of fentanyl and sufentanil (5-6min), and in contrast the slow onset time of morphine, where $t_{1/2}k_{e0}$ has been reported to exceed 4 hours.¹⁵ In addition, as reviewed in an editorial, when methadone is administered at a dose of 20mg or higher, the duration of analgesia approximates the half-life of 24-36 hours. Therefore, a single intravenous dose 20mg administered to an adult at induction of anaesthesia should provide a rapid onset and significant pain relief up to 1-2 days postoperatively, which is the period reported to have the highest pain score after cardiac surgery. Methadone is also a N-methyl-D-aspartate (NMDA) receptor antagonist. It has been reported to possess anti-hyperalgesic and anti-allodynic properties, that is important in preventing pain sensitization and the development of CPSP,¹⁶⁻¹⁷ which is of high risk in cardiac surgical patients.

SIDE EFFECTS OF METHADONE

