Only a few trials have studied intravenous methadone as an analgesic in surgical patients, in particular, there have not been many studies in the field of cardiac anaesthesia. A randomized controlled trial done by Murphy et al showed intraoperative methadone to be superior to fentanyl for patients undergoing cardiac surgery.²⁰ Methadone was demonstrated to reduce morphine consumption in the first 24 postoperative hours and improved pain scores at 12h after extubation compared to patients receiving fentanyl. There was 40% reduction in morphine requirement during the first 24h after extubation, and the severity of postoperative pain was decreased by 30-40% during the first three days after cardiac surgery. There was only one study comparing the analgesic efficacy between methadone and morphine given at the time of induction in cardiac surgical patients.²¹ Methadone was shown to reduce opioid requirement at 24h postoperatively and significantly reduce the incidence of postoperative nausea and vomiting. So far there has not been any studies on using methadone for cardiac surgery in Chinese populations, and none on the role of methadone for prevention of chronic post-surgical pain in cardiac surgical patients. Substantial literatures have demonstrated the ethnic differences in pain perception and endogenous pain modulation is postulated to be a mechanism for ethnic differences. Studies comparing Caucasians and Asians, such as Chinese and Indians, generally demonstrated lower pain tolerance in Asian populations.²²⁻²³ The primary aim of this study is to evaluate the use of methadone on acute and chronic pain control after open cardiac surgery, compared with conventional opioid-based approach using morphine and fentanyl.

METHODS/DESIGN

Study population and design

This is a single-centre, double-blinded, pilot randomized controlled trial conducted at Prince of Wales Hospital, a university teaching hospital with 1650 beds in Hong Kong. All elective cardiac surgical patients will be admitted to a 23-bed ICU for early postoperative care and monitoring with 1:1 nursing at all times, with an expectation of discharge from ICU to a high-dependency cardiac ward within 24 hours after surgery. Currently 350-400 adults undergo elective coronary artery bypass graft and/or valvular surgery each year.

Randomization and concealment

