Key secondary outcomes include the postoperative pain scores measured by numerical rating scale (NRS) represented as AUC at rest and movement; the time successfully weaned to spontaneous breathing according to ASV; patient satisfaction score to pain within 72h after the operation; time to first morphine rescue; side effects of opioids including the number of episodes of postoperative nausea and vomiting; time to first bowel movement; the recovery from surgery in terms of length of ICU and hospital stay; and chronic postsurgical pain at 3 and 6 months assessed using the Douleur Neuropathique en 4 questionnaire (DN4). It is a ten items questionnaire and the Mandarin Chinese

version has been validated in previous study.²⁶ Each item of DN4 is assigned a score of 0 when the participant answered ‘no’ and a score of 1 when the participant answered ‘yes’. The total DN4 score ranges from 0 to 10, and a score ≥ 4 indicates a diagnosis of neuropathic pain.²⁷⁻²⁸

Data collection

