Patients will be screened the day before operation for eligibility. Eligible patients will be given the patients’ information sheets regarding the main aspects of the trial. Research nurses will then discuss with the patients in light of the information provided in the information sheets. Written informed consent will be obtained from patients willing to participate in the trial. All data is collected by research team members blinded to group assignment. Patient demographics and body mass index will be recorded. The time weaned to spontaneous breathing on ASV will be recorded. At 15min after tracheal extubation and at 8h, 12h, 24h, 48h and 72h post-extubation, pain score at rest and on coughing will be quantified using Numerical Rating Scale (NRS) from 0 to 10. Zero represents no pain at all while 10 points represents the worst pain ever. The time to first morphine rescue (in minutes after surgery) will be measured. The level of sedation will be measured using the Ramsay Sedation Scale (1 = anxious, agitated or restless, or both; 2 = co-operative, oriented and tranquil; 3= respond to command only; 4 = exhibit brisk response to light glabellar tap or loud auditory stimulus; 5 = exhibit sluggish response to light glabellar tap or loud auditory stimulus; 6 = exhibits no response), episodes of nausea and vomiting, and whether antiemetics are prescribed will also be recorded at the above time points. At the same time, patients will be asked to rate the overall satisfaction with pain management on a verbal analogue scale (0 = worst possible, 100 = best possible).

The Douleur Neuropathique en 4 questionnaire (DN4)²⁶ will be used to evaluate the presence of neuropathic pain at 3 and 6 months after surgery.

The following medical and surgical data during the hospital stays will be extracted from patient charts:

1. Patient demographics (age, gender, EuroScore)
2. Type of surgery
3. Duration of surgery and duration of cardiopulmonary bypass
4. ASV time to spontaneous breathing
5. Total morphine consumption at 24 and 72 hours after surgery
6. Episodes of nausea and vomiting, and use of rescue antiemetics
7. Length of ICU and hospital stay

		STUDY PERIOD									
		Post-allocation									
TIMEPOINTS	Enrolment	Baseline	OT	4h stop sedation	15min extubate	12h extubate	24h extubate	48h extubate	72h extubate	3-month postop	6-month postop
ENROLMENT:											
Eligibility screen			X								
Informed consent			X								
Demographic data			X								

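### Chronic postsurgical pain is defined as any persisting surgical pain, but at 3 and 6 months only the DN4 is collected, so non-neuropathic persistent pain cannot be separated from no pain

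*Protocol*

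**What the plan says.** The background section, before Challenges in Pain Management, states that "CPSP is defined as the persistence of pain at surgical site or referred area, at least 3 months following the surgical procedure". Nothing there limits the term to neuropathic pain. The mechanisms listed in the same paragraph include "nerve entrapment by sternal wires, sternal retraction, ribs fractures, and intercostal neuralgia".

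Gaps in the Literatures says the trial is meant "to evaluate the use of methadone on acute and chronic pain control after open cardiac surgery". It describes the evidence gap as there being "none on the role of methadone for prevention of chronic post-surgical pain in cardiac surgical patients".

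Under Outcome measures, Secondary outcomes, the key secondary outcomes include "chronic postsurgical pain at 3 and 6 months assessed using the Douleur Neuropathique en 4 questionnaire (DN4"). The DN4 is described as ten yes/no items with a total of 0 to 10, of which "a score ≥ 4 indicates a diagnosis of neuropathic pain". No score is linked to whether pain is present at all.

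Data collection describes the same measurement more narrowly: the DN4 "will be used to evaluate the presence of neuropathic pain at 3 and 6 months after surgery".

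In the assessment schedule (Figure 1), the DN4 is the only row marked at 3 and 6 months. Numerical rating scale (NRS) scores end at 72 hours after extubation, in both the text and the schedule.

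**The concern.** The outcome carries the name of a broad condition, but the instrument detects one subtype of it. Persistent pain without enough neuropathic features falls below the cut-off, where it sits with complete absence of pain.

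Two misreadings could follow. A null DN4 result reported as a CPSP result could hide an effect on non-neuropathic persistent pain. A positive DN4 result could be presented as prevention of CPSP when only the neuropathic part was studied. The protocol offers CPSP prevention in cardiac surgery as a gap in knowledge, so readers are likely to look for exactly that answer.

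This cannot be left to a statistical analysis plan. It is a gap in what is collected, and no later analysis can recover a question that was not asked.

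**Working it through.** The protocol gives no figure for this outcome, so there is none to reproduce. The check has two parts.

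**1. Definition against data collected**

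| Element | Where | Scope |
|---|---|---|
| Definition of CPSP | Background | Any persisting pain, operated or referred area, from 3 months |
| Aim | Gaps in the Literatures | Chronic pain control, without subtype |
| Outcome name | Secondary outcomes | CPSP at 3 and 6 months |
| Instrument and cut-off | Secondary outcomes | DN4 ≥4, neuropathic pain |
| Stated purpose of the DN4 | Data collection | Presence of neuropathic pain |
| Other items at 3 and 6 months | Schedule | None |
| Last NRS | Data collection, schedule | 72 h after extubation |

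The first three rows are broad and the next two are narrow. The last two show that no other planned item fills the difference. The Figure 1 legend also expands abbreviations for a Neuropathic Pain Questionnaire and a pain catastrophizing scale. Neither has a row or time point in the schedule, so neither adds data at 3 or 6 months.

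**2. Illustrative size**

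Inputs:
- N = 86 planned patients (Sample size calculation and statistical methods), 43 per arm if split equally, no drop-out.
- c = 28% to 56%, the CPSP incidence cited in the background for up to 2 years. Applying it at 3–6 months is an assumption.
- s = 20% to 50%, the neuropathic share of CPSP. This is an assumption; the protocol gives no value.

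Patients with CPSP = N × c:
- 86 × 0.28 = 24.1
- 86 × 0.56 = 48.2

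With an error-free DN4, patients with CPSP who score below 4 = N × c × (1 − s):
- Low: 24.1 × (1 − 0.5) = 12.0, or 6.0 per arm
- High: 48.2 × (1 − 0.2) = 38.5, or 19.3 per arm

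With DN4 sensitivity and specificity both assumed to be 80%, the share of CPSP patients flagged is 0.8 × s + 0.2 × (1 − s):
- s = 0.2: 0.16 + 0.16 = 0.32, so 48.2 × 0.68 = 32.7 not flagged
- s = 0.5: 0.40 + 0.10 = 0.50, so 24.1 × 0.50 = 12.0 not flagged

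On the 68 patients (34 per group) required before the drop-out allowance, with an error-free DN4:
- Low: 68 × 0.28 × 0.5 = 9.5
- High: 68 × 0.56 × 0.8 = 30.5

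Widening s to 10–70% on 86 patients, with an error-free DN4:
- Low: 86 × 0.28 × 0.3 = 7.2
- High: 86 × 0.56 × 0.9 = 43.3

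**The case against.** A neuropathic endpoint is a legitimate choice and fits part of the rationale. Methadone's NMDA antagonism is said to confer "anti-hyperalgesic and anti-allodynic properties, that is important in preventing pain sensitization and the development of CPSP", and the listed mechanisms include nerve entrapment and intercostal neuralgia. The broad definition is background text attributed to an international association, whereas the outcomes section states how the outcome will be assessed and says openly what the DN4 detects. The protocol never says that a score below 4 means no pain. This is one secondary outcome among several in a self-described pilot, with no sample size built on it, and the numbers above depend on a neuropathic share found nowhere in the document.

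Some of this stands. A DN4 endpoint is defensible if it is named as such, and the size is only illustrative. The mechanism list is supporting evidence at most, because the protocol does not sort its entries into neuropathic and non-neuropathic. The DN4 items are not reproduced either, so the claim rests on how the protocol describes the scale.

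The mismatch itself is not answered. The outcome is called CPSP, the only CPSP definition in the protocol is the broad one, and the aim is worded for chronic pain in general. That a score below 4 is given no meaning is the difficulty itself: nothing else collected supplies one.

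**Conclusion.** The concern holds. Followed exactly, the plan yields the frequency of DN4 ≥4 at 3 and 6 months, not the frequency of CPSP as the protocol defines it. The chronic-pain aim is then answered only for its neuropathic part.

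Confidence is high for the mismatch, which is a direct comparison of the protocol's own statements. It is low for the size. About 12 to 39 of 86 patients could have persistent pain yet score below 4, or about 7 to 43 under a wider assumed share. Both ranges assume that the cited incidence applies at 3–6 months, that follow-up is complete and that the DN4 is error-free.

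The primary outcome, sample size and safety are unaffected. The change should be made, because it is cheap and the missing information cannot be obtained afterwards.

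**What to change.** At the 3- and 6-month contacts already planned, add one yes/no question on whether the patient has pain in the operated or referred area; an NRS score is optional. Define CPSP by a yes, in line with the background definition, and report DN4 ≥4 as its neuropathic component. Amend Secondary outcomes, Data collection and the schedule to match.

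If the narrower endpoint is intended, or no question can be added, rename the outcome in Secondary outcomes as neuropathic pain (DN4 ≥4) at 3 and 6 months, consistent with Data collection. Narrow the chronic-pain part of the aim in Gaps in the Literatures to match.

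The first option costs one short question and an amended outcome definition. Patients already past a contact will lack the item for that time point, so it should be added promptly and the missing answers reported. The second option changes wording only, but gives up the broader question.

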All patients will receive standard monitoring for cardiac surgery. General anaesthesia will be induced with midazolam 0.01-0.05mg/kg, fentanyl 2-5mcg/kg and rocuronium 0.5-1mg/kg to facilitate intubation with single-lumen cuffed endotracheal tube. Anaesthesia will be maintained with sevoflurane and propofol infusion that target Bispectral Index 40-60. The study drug (either methadone 0.2mg/kg or morphine at equipotent dose) in blind labelling will be administered at time of induction by intravenous infusion over 30 minutes. No further morphine will be given throughout the operation. No other analgesics (paracetamol, non-steroidal anti-inflammatory agents, dexmedetomidine, ketamine), steroids or antiemetics will be given intraoperatively. Patient-controlled analgesia (PCA) morphine protocol will be prescribed to patients for 72 hours after operation for postoperative analgesia. Oral analgesics including paracetamol 1g every 6 hours and dihydrocodeine 30mg three times a day will be prescribed by parent surgical team. At the end of the operation, the patients will be kept sedated with propofol infusion to ICU. Propofol infusion will be stopped upon admission to ICU to facilitate weaning from ventilator. Adaptive Support Ventilation (ASV) is used in ICU for weaning which adjusts the ventilation parameters depending on the patient's lung mechanics and effort. Pain will be assessed by nurses in ICU at 4h after stopping sedation, then once every 2h. Upon extubation, patient will be assessed the pain score and the level of sedation at 15min, 8h, 12h, 24h, 48h and 72h. 1mg morphine will be administered via PCA to patients if pain of more than mild severity was noted. Any nausea or vomiting, and use of rescue antiemetics will be documented.

Outcome measures

Primary outcomes

The most intense pain typically occurs in the first 2-3 days after open heart surgery, leading to greater need for analgesia during this period. The primary outcome will be set at 72-hour time frame based on the postoperative morphine consumption.

Secondary outcomes

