Comorbidity data			X								
EuroScore			X								
Allocation			X								
INTERVENTIONS											
Intraoperative methadone				X							
Intraoperative morphine				X							
OUTCOMES:											
Ramsay sedation scale				X	X	X	X	X	X		
NRS score				X	X	X	X	X	X		
ASV time to spontaneous breathing					X						
DN4										X	X
Time to first morphine rescue						X	X	X	X		
Postoperative morphine consumption						X	X	X	X		
Patient satisfaction						X	X	X	X		
Use of rescue antiemetics						X	X	X	X		
Nausea/vomiting						X	X	X	X		
Time to first bowel movement						X	X	X	X		
ICU and hospital stay									X		

Figure 1 Assessments overview. NRS, numerical rating scale; ASV, adaptive support ventilation; NPQ, Neuropathic Pain Questionnaire; HK-PCS, Pain Catastrophizing Scale Hong Kong version.

Blood sampling for methadone level

Venous blood samples (5ml) will be obtained at 0, 1, 2, 4, 6, 8, 10, 12, 24, 48, 72 and 96 hours after administration of methadone. Plasma concentration of methadone will be determined by LC-MS/MS (ESI pos). The internal standard (7-dimethylamino-5,5-diphenyl-4-octanone, 2.5ng) will be added to plasma (0.5ml), which will be acidified and then processed by SPE (Waters Oasis MCX cartridges).

Sample size calculation and statistical methods

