The sample size is calculated using G*Power software version 3.1.9.3 (Kiel University, Kiel, Germany), and based on postoperative morphine consumption at 24 hours, which is the primary outcome variable. Because there was no randomized controlled trial on use of methadone in cardiac surgery in Asian population, a pilot study (50 patients) was conducted from cardiac surgical patients in Prince of Wales Hospital, Hong Kong. The mean (SD) postoperative morphine consumption at 24 hours was 21.5 (8.2) mg in patients receiving methadone, whereas that for morphine group was 30.3 (14.0) mg. With an alpha probability of 0.05 and a power of 90%, a sample size of 34 patients in each group will be needed. Assuming 15% drop-out rate, the sample size is increased to 86 patients. The primary analyses will be performed on a modified intention-to-treat basis. Patients will be analysed according to their randomized allocated groups but will be excluded from the analysis if they do not adhere to the protocol after randomisation. Categorical data are reported as numbers and percentages. Continuous variables are reported as mean (standard deviation) or median (interquartile range) as appropriate after checking for normality using the Shapiro-Wilk's test. Comparison of continuous data is performed by Student's *t* test and by Mann-Whitney U test for non-normally distributed data. Chi-square test is used to compare groups with categorical variables. Level of significance is set at P<0.05. SPSS 27.0 software (IBM Corp, Armonk, NY) will be used for data analysis.

DECLARATIONS

Consent to participate

All participants will provide written informed consent. All research will be conducted in accordance with the Declaration of Helsinki and all other relevant guidelines and regulations.

Consent for publication

Not applicable

Competing interests

The authors declare that they have no competing interests.

Funding

This work was funded by the Health and Medical Research Fund from the Health Bureau of the Government of HKSAR (Reference number: 10211156), and internally supported by the Department of Anaesthesia and Intensive Care, The Chinese University of Hong Kong. This funding has no role in the design of this study and will not have any role during its execution, analyses, interpretation of the data, or decision to submit results.

REFERENCES

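### Time to first bowel movement is recorded only to 72 h after extubation, and the stated tests give no way to use a patient who has not had the event by then

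*Protocol*

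**What the plan says.** - **Outcomes.** Protocol, Secondary outcomes, lists "time to first morphine rescue; side effects of opioids including the number of episodes of postoperative nausea and vomiting; time to first bowel movement" among the key secondary outcomes.
- **Time origin.** Data collection gives an origin and unit for one of the two times: "The time to first morphine rescue (in minutes after surgery) will be measured". No origin, unit or end of observation is given for bowel movement.
- **Window.** In Figure 1 the row "Time to first bowel movement" is marked at 12, 24, 48 and 72 h after extubation and at no later visit. The row for first morphine rescue has the same marks. The PCA morphine "protocol will be prescribed to patients for 72 hours after operation for postoperative analgesia".
- **Other sources.** The list in Data collection of items extracted from charts includes length of ICU and hospital stay. It does not include bowel movement.
- **Tests.** Sample size calculation and statistical methods compares continuous data by Student's t test, or "by Mann-Whitney U test for non-normally distributed data". For the rest, "Chi-square test is used to compare groups with categorical variables". No time-to-event method is named, and nothing is said about a patient in whom the event is not observed. The only stated exclusion concerns patients who do not adhere to the protocol after randomisation.

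**The concern.** A time to an event, watched for a limited period, is known exactly only for patients who have the event in that period. For the others it is known only to exceed the last observation. The protocol places such an outcome under tests that take one number per patient and gives no number or rank for a patient still waiting at 72 h.

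The easiest course in the analysis is then to leave the value missing. For bowel movement this removes the slowest recoveries, and it removes more of them from the slower arm. What remains is a comparison among patients who recovered within the window, so a real difference between arms looks smaller and is harder to detect. If the handling is left open, it could also be settled after the data have been seen.

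**Working it through.** The protocol gives no figure for bowel movement, either a rate or an effect, so there is no stated figure to reproduce. The event-free shares below are assumptions.

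**Inputs.** From the protocol: 86 patients and 15% drop-out, so 86 × 0.85 = 73.1, or 36 to 37 per arm (36 used); two-sided 5% level (the protocol gives 0.05 without stating sides); observation to 72 h. Assumed: exponential times, a common 72 h cut-off, and event-free shares q at 72 h of 2% against 10% and of 10% against 30% (faster against slower arm).

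**Step 1: effect on the medians.** The rate is λ = −ln(q)/72. The true median is ln(2)/λ. The median among patients who have the event by 72 h is −ln((1 + q)/2)/λ.

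| q at 72 h | λ per hour | True median | Median if event-free patients are dropped |
|---|---|---|---|
| 2% | 0.0543 | 12.8 h | 12.4 h |
| 10% | 0.0320 | 21.7 h | 18.7 h |
| 30% | 0.0167 | 41.5 h | 25.8 h |

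The gaps, from unrounded values, are:
- 2% against 10%: 8.9 h true, 6.3 h after dropping.
- 10% against 30%: 19.8 h true, about 7 h after dropping.

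**Step 2: effect on power.** Trials were simulated with 36 per arm and analysed in three ways.

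| Event-free shares | Rate ratio | Mann-Whitney, event-free dropped | Mann-Whitney, event-free ranked worst | Log-rank, event-free censored |
|---|---|---|---|---|
| 2% / 10% | 1.7 | 0.30 | 0.48 | 0.58 |
| 10% / 30% | 1.9 | 0.18 | 0.60 | 0.68 |

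A repeat run with other random numbers agreed to within about 0.02.

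**Step 3: sensitivity.** With 34 per arm and an assumed hazard ratio of 0.5, the same three powers, by the event-free share in the slower arm, are:
- 2%: 0.64, 0.67 and 0.79.
- 20%: 0.30, 0.67 and 0.77.
- 50%: 0.09, 0.57 and 0.61.

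Weibull times with shape 2 give nearly the same values. The loss therefore depends on how many patients are event-free, and little on the shape of the distribution.

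**Step 4: first morphine rescue.** The pilot mean (SD) 24 h consumption is 21.5 (8.2) mg with methadone and 30.3 (14.0) mg with morphine. A normal approximation to the share at or below zero gives Φ(−21.5/8.2) = Φ(−2.62) = 0.4% and Φ(−30.3/14.0) = Φ(−2.16) = 1.5%. A gamma model with the same means and SDs puts under 0.001% below 1 mg. Almost every patient should have had a first rescue by 24 h, well inside the window.

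**The case against.** - **Dropping is not written.** A reader might infer that the protocol instructs the analyst to leave out event-free patients. It does not. The only exclusion rule concerns adherence, and the methods paragraph names neither time outcome. This objection stands, and the loss above is conditional on that handling.
- **Mann-Whitney does not force the loss.** It needs an ordering, and event-free patients can share the worst rank. This also stands: in the 10%/30% case, keeping patients raises power from 0.18 to 0.60, and log-rank adds only a further 0.08. That last gain is also obtained with simulated data that have proportional hazards. But the protocol does not specify worst ranks, and the t test has no such remedy.
- **First rescue is hardly touched.** A reader might infer that both time outcomes are distorted. Step 4 shows that the protocol's own pilot figures do not support this.
- **The 72 h end is read from Figure 1 alone.** That column is the last one in hospital. ICU and hospital stay is also marked only there, although a stay need not end then. This weakens the reading in part. Length of stay, however, is also on the chart-extraction list, whereas bowel movement has no other listed source.
- **The event-free shares are invented and the effects are large.** This is true: the documents give no rate. If almost all patients have the event by 72 h, little is lost.
- **An analysis plan may settle this.** It may. But the protocol is not silent: it commits continuous data to two named tests, and a later plan would have to depart from or add to that text.

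**Conclusion.** The point holds for time to first bowel movement, at low severity. The protocol schedules this outcome to 72 h after extubation, lists no later source, and names tests without a rule for patients who have not had the event.

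If those patients were treated as missing, the contrast would shrink towards no difference. Under the assumed shares, power would be about 0.30 (2%/10%) or 0.18 (10%/30%), against 0.48 and 0.60 with worst ranks and 0.58 and 0.68 with log-rank. These figures rest on exponential times, a common cut-off, 36 per arm and event-free shares that the documents do not give. Most of the loss comes from dropping patients, not from the choice of Mann-Whitney.

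Time to first morphine rescue is affected negligibly and is mentioned only so that the two outcomes are handled alike. The primary outcome is not affected.

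**What to change.** In Sample size calculation and statistical methods, state that time to first bowel movement (and, for consistency, time to first morphine rescue) is measured from end of surgery and analysed by Kaplan-Meier curves and the log-rank test. Report a hazard ratio with its 95% CI, and censor event-free patients at their last assessment. Because recording is scheduled from extubation while the time runs from surgery, patients will be censored at slightly different times, which this method handles directly.

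An acceptable fallback is to keep Mann-Whitney and specify in advance that event-free patients receive the worst rank for bowel movement.

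The cost is a sentence or two, with no new data collection and no change to the sample size. The downside is that a hazard ratio is reported beside the medians. The text should be in place before unblinding.

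### The sample-size figures do not agree: 34 per group with 15% drop-out gives 80, not 86, and on the stated means and SDs 34 per group has 87.6% power, not 90%

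*Protocol*

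**What the plan says.** All the figures are in the protocol under 'Sample size calculation and statistical methods'. The calculation was done in G*Power and uses morphine consumption at 24 hours from a 50-patient pilot at the same hospital.

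- Methadone arm: "The mean (SD) postoperative morphine consumption at 24 hours was 21.5 (8.2) mg in patients receiving methadone".
- Morphine arm: "whereas that for morphine group was 30.3 (14.0) mg".
- Error rates: alpha 0.05 and power 90%.
- Result and allowance for loss: "a sample size of 34 patients in each group will be needed. Assuming 15% drop-out rate, the sample size is increased to 86 patients".

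The same section names Student's t test for continuous data, with the Mann-Whitney U test if the data are not normal, and adds "Level of significance is set at P<0.05". It does not say whether the test is one- or two-sided, how the two SDs were combined, or what effect size was entered in the software.

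**The concern.** Two steps lead from the pilot data to 86 patients, and neither reproduces. The first takes the pilot means and SDs to 34 per group; the second takes 34 per group and 15% loss to 86. At least one of the required number, the power, the loss rate or the total must therefore be wrong as printed.

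The number that matters for power is the evaluable number. The primary analysis is a modified intention-to-treat analysis that drops patients who depart from the protocol after randomisation, so the evaluable number can be expected to fall below the number randomised. A team that reads 34 per group as sufficient would accept 68 evaluable patients and less than the stated power. A reader of the protocol also cannot tell which loss rate the trial was planned to absorb.

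**Working it through.** **Inputs (all from the protocol's sample-size section).** Means 21.5 and 30.3 mg; SDs 8.2 and 14.0 mg; alpha 0.05; power 90%; equal groups; 15% loss; Student's t test. **Assumption:** two-sided test. The one-sided result is given as well.

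**Step 1: the drop-out step, which needs no assumption about the test.**

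- Evaluable total: 2 × 34 = 68.
- Dividing by the retained fraction: 68/0.85 = 80 (34/0.85 = 40 per group).
- Multiplying by 1.15: 68 × 1.15 = 78.2, so 79. By arm, 34 × 1.15 = 39.1, so 40 per group and 80 in total.
- Loss implied by 86: 1 − 68/86 = 0.209, or 20.9%.

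Neither rule gives 86.

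**Step 2: the effect size.**

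- Difference: 30.3 − 21.5 = 8.8 mg.
- With n per group, the variance of the difference in means is (8.2² + 14.0²)/n = (67.24 + 196)/n. The matching common SD is √(263.24/2) = √131.62 = 11.47 mg.
- d = 8.8/11.47 = 0.767.

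**Step 3: power and required number (noncentral t, two-sided 0.05).** The noncentrality is d × √(n/2), with 2n − 2 degrees of freedom. At n = 34 it is 0.767 × √17 = 3.16.

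| Evaluable per group | Power |
|---|---|
| 34 | 87.6% |
| 36 | 89.4% |
| 36 and 37 (73 in total) | 89.8% |
| 37 | 90.2% |

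So 90% power needs 37 per group, 74 in total: 6 more than 68, or about 9%.

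**Step 4: can another method produce 34?**

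| Method | n per group for 90% | Power at 34 |
|---|---|---|
| t test, two-sided | 37 | 87.6% |
| Welch t test, two-sided | 37 | 87.4% |
| Normal approximation, two-sided | 36 | 88.5% |
| t test, one-sided | 30 | 93.1% |
| Mann-Whitney, two-sided (usual efficiency factors) | 39 to 43 | – |
| Mann-Whitney, one-sided (usual efficiency factors) | 32 to 35 | – |
| SDs averaged to 11.1 (d = 0.793), t test, two-sided | 35 | 89.6% |
| SDs averaged to 11.1, normal approximation, two-sided | 34 | 90.5% |
| d rounded up to 0.80, t test, two-sided | 34 | 90.2% |

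Thirty-four can be reached by rounding d up, or by averaging the SDs rather than the variances and using a normal approximation. A one-sided Mann-Whitney calculation also spans it. The protocol states none of these.

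**Step 5: where 86 could come from.** 86 is 43 per group.

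- 37 × 1.15 = 42.55, which rounds up to 43.
- 36/0.85 = 42.4, which also rounds up to 43.

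The total therefore fits a requirement of 36 or 37 per group, and 34 is the likelier misprint or miscalculation.

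**Step 6: what 86 delivers.** 86 × 0.85 = 73.1, so about 73 evaluable patients and 89.8% power (step 3). Dividing 37 by 0.85 gives 43.5, so 44 per group, or 88 in total.

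**The case against.** The best counter-argument is that the power part depends on an SD the protocol never specifies. The pilot's group sizes are not given, and pooling weighted by degrees of freedom from an uneven pilot could give a smaller SD. With 29 methadone and 21 morphine patients the pooled SD would be √((28 × 67.24 + 20 × 196)/48) = 10.99, d would be 0.800, and 34 per group would have 90.2% power. The gap is in any case only 2.4 points, which is small beside the sampling error of SDs from 50 patients. The drop-out error also runs in the safe direction: 86 is six more than 80, and nothing in the plan stops recruitment at 68 evaluable.

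Part of this stands. Thirty-four may well have come from a d near 0.80, the shortfall is modest, and a trial that randomises 86 comes very close to its stated power.

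The pilot-split argument does not rescue 34, however. If the arms have SDs of 8.2 and 14.0, a trial with equal groups has the equal-weight average of the two variances, whatever the split in the pilot. Weighting towards the less variable arm understates the variance of the planned comparison. The mismatch between 34, 15% and 86 does not depend on the SD at all, and nothing elsewhere in the protocol explains it.

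**Conclusion.** The concern holds. The drop-out inconsistency is firm and needs no assumption: 34 per group with 15% loss gives 79 or 80, not 86, and 86 would imply 20.9% loss. The power inconsistency is smaller. It rests on a two-sided Student's t test and on taking the two SDs at face value in a trial with equal groups. On that basis 34 per group has 87.6% power, and 90% needs 37 per group. A one-sided t test does not recover 34.

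The design is barely affected, because 86 randomised with 15% loss keeps 89.8% power on the same assumptions. What fails is the statement of the calculation, which should be corrected because it sets the evaluable target.

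**What to change.** Rewrite the sentence so that the figures follow from one another. State a two-sided alpha of 0.05 (if that is what was intended), the common SD of 11.47 mg, d = 0.767, and 37 evaluable patients per group (74) for 90% power. Then keep 86 and say that 15% loss leaves about 73 evaluable patients with 89.8% power. If the sponsor prefers to keep 34 per group, pair it with 87.6% power and correct either the loss rate or the total, since 15% loss would then give 80. Raising the total to 88 would meet 90% in full but is not needed for a difference of 0.2 points.

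If a different SD or effect size was entered in the software, state and justify it, and make 34, 15% and 86 agree with it.

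The cost is one sentence in the protocol. With 86 retained, no patients are added and nothing in the conduct of the trial changes.
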